4.6 Secondary objective #2: Frequency of exacerbations during observation

Table 24. Exacerbations since IPF diagnosis

This table will describe the absolute and relative frequency distribution of patients with:

- at least one exacerbation during observation period since IPF diagnosis [\[F08_EXACERBATIONS.EX_Exacerbation_YN\]](#)
- at least one mild, moderate, severe exacerbation during observation period since IPF diagnosis [\[F08_EXACERBATIONS.Ex_exacer_1-10_Severity\]](#)

Percentages will be computed out of the total number of patients evaluable at enrollment.

The table will provide the descriptive statistics (mean, median, standard deviation, quartiles, min, max) of

- number of exacerbations per patient since IPF diagnosis during observation period (as defined in “Computed variables” chapter)
- number of exacerbations per patient since IPF diagnosis during observation period stratified by exacerbation severity [\[F08_EXACERBATIONS.Ex_exacer_1-10_Severity\]](#)

Descriptives will be calculated out of the number of patients evaluable at enrollment.

4.7 Secondary objective #3: Health related quality of life (HRQoL) variation during 12 months of observation

Table 26. EQ-5D-5L distribution of items of descriptive system and VAS during observation

The table will provide at enrollment, V3, V5:

- Frequency or the proportion of reported problems for each level for each dimension: mobility, self-care, usual activity, pain/discomfort, anxiety/depression [F11_EQ_5D_5L.EQ_5d_1-EQ_5D_5]
- main descriptive statistics (mean, median, standard deviation, quartiles, min, max) of EQ VAS [F11_EQ_5D_5L.EQ_5d_6_NUM]

Descriptives will be calculated over the number of patients who performed each visit with EQ-5D-5L filled in.

Higher index and VAS scores mean better QoL.

Table 27. St.Georges Respiratory Questionnaire (SGRQ)

The table will provide at enrollment, V3, V5 the descriptive statistics (mean, median, standard deviation, quartiles, min, max) of the:

- 3 components scores of SGRQ: symptoms, activities and impacts on daily life;
- total score (as defined in "Computed variables" chapter).
- change at each follow-up visit vs baseline of symptoms, activities and impacts on daily life scores;
- change at each follow-up visit vs baseline of total score.

Descriptives will be calculated over the number of patients who performed each visit with SGRQ filled in.

4.8 Secondary objective #4: Healthcare resource utilization from diagnosis up to the end of 12-month follow-up

Table 28. Hospitalizations (inward/day hospital) and ICU admissions for IPF, IPF EXACERBATIONS OR IPF-RELATED ADVERSE EVENTS

The table will provide the distribution of patients with at least

- one hospitalization (inward/day hospital) [F20_RESOURCE_CONS.RES_Hosp_matrix_1_Inw-RES_Hosp_matrix_12_Inw]
- one ICU admission [F20_RESOURCE_CONS.RES_Hosp_matrix_1_ICU_YN-RES_Hosp_matrix_12_ICU_YN]

for IPF, IPF exacerbations or IPF related adverse events from diagnosis to the end of observation period.

Analyses will be computed out of the total number of patients evaluable at enrollment.

Table 29. Number of hospitalizations (inward/day hospital) and admissions to ICU and Overall duration of admission

The table will provide the distribution of patients by number of hospitalizations received from diagnosis to the end of observation period by type of admission (inward/day hospital) and number of admissions to ICU.

Analyses will be computed out of the total number of patients evaluable at enrollment.

The table will provide the descriptive statistics (mean, median, standard deviation, quartiles, min, max) of overall duration of admissions [F20_RESOURCE_CONS.RES_Hosp_matrix_1_Adm,RES_Hosp_matrix_12_Adm;F20_RESOURCE_CONS.RES_Hosp_matrix_1_adm_icu-RES_Hosp_matrix_12_adm_icu].

Statistics computed over the total number of admissions received since IPF diagnosis till end of observation period, overall and stratified by type of admission (inward/day hospital, ICU).

Analyses will be computed out of the total number of patients evaluable at enrollment.

Table 30. Emergency room accesses

The table will provide

- Distribution of patients with at least one emergency room access for IPF, IPF exacerbations or IPF related adverse events from diagnosis to the end of observation period [F20_RESOURCE_CONS.RES_ER_YN];
- Distribution of patients by number of ER accesses per patient [F20_RESOURCE_CONS.RES_ER_Matrix_1_n_accesRES_ER_Matrix_8_n_acc] from diagnosis to the end of observation period.

Statistics computed over the total number of ER admissions received from diagnosis to the end of observation period.

Analyses will be computed out of the total number of patients evaluable at enrollment.

Table 31. Specialist and general practitioner outpatient visits

The table will provide

- Distribution of patients with at least one specialist or general practitioner outpatient visit for IPF, IPF exacerbations or IPF related adverse events [F20_RESOURCE_CONS.RES_OUTP_YN] from diagnosis to the end of observation period;
- Distribution of patients by type of specialist outpatient visits [F20_RESOURCE_CONS.Specialist,RES_other_Specialist] performed from diagnosis to the end of observation period. One patient could perform more than one type of specialist outpatient visit. A patient who performed the same type of visit more than once will count one.
- Descriptive statistics (mean, median, standard deviation, quartiles, min, max) of the number of specialist outpatient visits per patient (overall and by visit type) [F20_RESOURCE_CONS.RES_Nr_Visits] from diagnosis to the end of observation period.

- Descriptive statistics (mean, median, standard deviation, quartiles, min, max) of the number of GP visits for IPF, IPF exacerbations or IPF related adverse events per patient [\[F20_RESOURCE_CONS.RES_GP_Visit_YN_Num\]](#) from diagnosis to the end of observation period.

Analyses will be computed out of the total number of patients evaluable at enrollment.

Table 32. Patients who performed laboratory tests

The table will provide

- Distribution of patients with at least one laboratory test for IPF, IPF exacerbations or IPF related adverse events from diagnosis to the end of observation period [\[F20_RESOURCE_CONS.RES_LAB_TEST_YN\]](#)

Analyses will be computed out of the total number of patients evaluable at enrollment.

Table 33. Laboratory tests: number and type

The table will provide

- Descriptive statistics (mean, median, standard deviation, quartiles, min, max) of the number of laboratory tests per patient [\[F20_RESOURCE_CONS.RES_LAB_matrix_1_ex-RES_LAB_matrix_10_ex\]](#); [\[F20_RESOURCE_CONS.RES_LAB_matrix_1_num-RES_LAB_matrix_10_num\]](#) from diagnosis to the end of observation period, overall and stratified by type of test/examination.

Analyses will be computed out of the total number of patients evaluable at enrollment.

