The absolute and relative frequency distributions of patients (N, %) according to ongoing comorbidities (such as gastroesophageal reflux disease, pulmonary hypertension, emphysema, lung cancer, coronary heart disease, depression) will be also provided at baseline.

Treatment modalities will be described at each visit by means of frequency distribution of patients according to ongoing therapies for IPF; pharmacological (such as steroids, anticoagulants, immunomodulators, N-acetylcysteine, pirfenidone, etc..) and non-pharmacological (such as long term oxygen and pulmonary rehabilitation) therapies will be considered and described in terms of drug, dosage regimen and duration/number of sessions (including start and stop dates). The frequency of patients on listing for lung transplantation at baseline will be also provided.

#2 To describe the frequency of exacerbations during 12 months of observation

The proportion of patients with at least one exacerbation after 12 months of observation will be computed as the ratio between the number of patients with one or more episodes of

exacerbation occurred during 12 months of follow up over the total number of evaluable patients. Patients who drop-out without having exacerbations before the end of the study, will be considered in the denominator of the proportion of interest. The median number of episodes of exacerbation per patient will be provided. Finally time to first exacerbation will be analyzed by Kaplan-Meier curves.

#3 To describe the HRQoL variation during 12 months of observation

The digits for EQ-5D-5L 5 dimensions can be combined in a 5-digit number describing the respondent's health state. An appropriate algorithm will be used to summarize data in an overall score ranging from -1 (worse-than-death health status) to 1 (best health status) [38, 48].

The descriptive statistics will be produced for EQ-5D-5L descriptive system index and VAS. Moreover, the difference of scores between baseline and available follow up visits will be calculated too.

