1 STATISTICAL ANALYSIS PLAN OBJECTIVES

The FIBRONET study is a multi-center, non-interventional (observational) prospective cohort study based mainly on newly collected data. A total of 200 consecutive patients will be enrolled in approximately 18 months (from the first patient enrolled). Patients will be followed-up for 1 year, with 3 intermediate evaluations after 3 (± 1), 6 (± 1) and 9 (± 1) months since baseline (which is compatible with current clinical practice in Italy for IPF patients management).

The present Statistical Analysis Plan has been designed considering the following input documents: the Study Protocol v.1.0 26/06/2015 and the electronic case report form v. 1.1.1 30/11/2015.

This SAP is aimed at evaluating the following study objectives:

Primary objective:

1. In a sample of IPF diagnosed patients to describe the clinical course during 12 months of observation, in terms of:
 - IPF symptoms
 - lung function (VC, FVC, FEV1, TLC, DLCO, pO₂, pCO₂; SaO₂, PaO₂ and PaCO₂ at rest)
 - exercise tolerance (6-minute walk distance test)

Secondary objectives:

1. Description of characteristics of IPF patients at enrollment in terms of:
 - key (socio-) demographic data
 - IPF risk factors, comorbidities
 - IPF disease severity and manifestation (including lung function, cardiopulmonary exercise testing and/or exercise capacity if available, laboratory values)
 - Methods used for IPF diagnosis
 - IPF treatment modalities (detailed information on prescribed drugs and dose; non-pharmacological treatment; lung transplantation)
2. To describe the frequency of exacerbations during 12 months of observation.
3. To describe HRQoL variation, measured with SGRQ, EuroQol (EQ) 5-dimension 5-level (EQ-5D-5L) descriptive system and EQ VAS, during 12 months of observation.
4. To describe health care sector-related costs from diagnosis up to the end of 12-month follow-up according to the Italian National Health Service (INHS) point of view.

The ongoing (pharmacological and non-pharmacological) therapies at each follow up
will be described too.

In this document the eCRF fields are indicated as follows: "label of the field" [[name of the eCRF form.name of the variable in the dataset](#)].

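### SAP Table 26, as published, lists no within-patient change in EQ VAS and no visible EQ-5D-5L index, although protocol section 8.7 asks for both

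*SAP*

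**What the plan says.** The SAP (section 1) keeps the protocol's third secondary objective: "To describe HRQoL variation, measured with SGRQ, EuroQol (EQ) 5-dimension 5-level (EQ-5D-5L) descriptive system and EQ VAS, during 12 months of observation". Three measures are named, and the target is variation.

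Protocol section 8.7, under objective #3, sets out the EQ-5D-5L analysis. The five digits are to be turned into a single score: "An appropriate algorithm will be used to summarize data in an overall score ranging from -1" upward to 1, with two references cited. Then "The descriptive statistics will be produced for EQ-5D-5L descriptive system index and VAS", and in addition "the difference of scores between baseline and available follow up visits will be calculated too". The protocol synopsis repeats the last two requirements. Section 8.7 also asks for graphs of mean scores by visit.

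SAP section 4.7 implements this in two tables.

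- Table 26 (EQ-5D-5L) has two rows at enrolment, V3 and V5: the frequency of each response level in each dimension, and "main descriptive statistics (mean, median, standard deviation, quartiles, min, max) of EQ VAS". The denominator at each visit is the patients who performed that visit and filled in the form. A note below reads "Higher index and VAS scores mean better QoL".
- Table 27 (SGRQ) gives the three components and the total at the same visits. It then adds the change from baseline for each component and "change at each follow-up visit vs baseline of total score".

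**The concern.** The two tables serve the same objective but are built differently. SGRQ gets within-patient change. EQ VAS gets only its level at each visit, although its change is a simple subtraction that the protocol asks for. The index does not appear as a row, yet the note under Table 26 explains how to read one.

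If the SAP is followed as printed, variation in EQ VAS has to be read by comparing visit means. Those means come from different patients. The protocol expects 20% to 40% to be lost by month 12, and section 8.5 says this rate allows for mortality, so leavers are plausibly sicker at baseline. SAP section 3 narrows the set further: a visit counts as performed only if it falls within 1.5 months of target and symptom data exist both at baseline and at that visit. A stable or rising mean could then reflect who is left rather than how patients fared. The spread of individual change would not be reported either.

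**Working it through.** **1. Row check against protocol 8.7 #3**

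| Measure | Level by visit | Change from baseline |
|---|---|---|
| SGRQ components and total | Table 27 | Table 27 |
| EQ VAS | Table 26 | not listed |
| EQ-5D-5L dimensions | Table 26 (frequencies) | not applicable as a score |
| EQ-5D-5L index | not visible | not visible |

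So one of the three measures named in the objective has a visible change-from-baseline summary. SAP section 3 describes the two parts of EQ-5D-5L but shows no index derivation, and points to an Appendix 8.3 that is not in the published text.

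**2. The plan's own figure**

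Protocol 8.5: 200 patients with 20% to 40% drop-out. 200 × (1 − 0.20) = 160 and 200 × (1 − 0.40) = 120. These match the stated 120 to 160 evaluable patients at month 12.

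**3. Shift in the difference of visit means when no patient changes**

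Let *d* be the drop-out share, *g* the baseline VAS gap (completers minus leavers) and *m* the completers' baseline mean.

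- Baseline mean, all patients: (1 − *d*)·*m* + *d*·(*m* − *g*) = *m* − *d*·*g*
- Month-12 mean, completers with no change: *m*
- Apparent change: *d* × *g*

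The documents give no EQ VAS figure, so *g* is an assumption, shown over a range:

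| Gap *g* (points) | *d* = 20% | *d* = 40% |
|---|---|---|
| 5 | 1 | 2 |
| 10 | 2 | 4 |
| 15 | 3 | 6 |

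The paired change in patients with both values is zero in every cell, which is the true change in those patients.

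**4. What visit summaries cannot supply**

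With equal SD at both visits and within-patient correlation ρ, the SD of change is SD × √(2(1 − ρ)). The published rows do not give ρ. For assumed ρ from 0.3 to 0.8 the SD of change runs from 1.18 to 0.63 SD, so it cannot be recovered from the visit SDs.

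The 95% half-width of the mean paired change is 1.96 × SD of change / √n:

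- n = 120: 0.212 SD (ρ = 0.3) to 0.113 SD (ρ = 0.8)
- n = 160: 0.183 SD to 0.098 SD

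Treating the visit means as independent, with 200 at baseline, gives 1.96 × √(1/200 + 1/n) = 0.226 SD at n = 120 and 0.208 SD at n = 160. The paired row is therefore also more precise over this range of ρ.

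**The case against.** **The published SAP is incomplete.** Table numbers jump from 13 to 20, from 22 to 24 and from 24 to 26, and sections 4.3, 4.5 and 4.13 do not appear. Rows may be gone too: section 3 defines changes for VCin and RV, but Table 20 lists neither. The note under Table 26 could be what remains of an index row. This stands for the index. A reader might infer that the plan has no index, but the documents do not settle that, so it can only be a query. The argument is much weaker for the VAS change. Table 26 has a title, rows, denominator and note with no visible gap. Its title names only the items and the VAS, and Table 27 follows directly with its change rows in place.

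**The protocol already specifies the analysis.** The SAP names protocol v1.0 as an input, and nothing visible withdraws the requirement. That is so, and it makes this a misalignment rather than an abandoned analysis. But the SAP lists the tables to be produced, and an unlisted row may not be programmed.

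**Visit means are themselves planned.** The protocol asks for graphs of them. It asks for differences from baseline as well, so one does not replace the other.

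**Paired change is still a completer result.** Correct. It removes the change in cohort composition but says nothing about patients who died or left before the visit.

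**Conclusion.** The concern holds for EQ VAS: the published Table 26 omits a change from baseline that protocol 8.7 requires and that the SAP supplies for SGRQ. For the EQ-5D-5L index and its change, the finding is that they are not visible and need confirming.

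A reader might go further and infer that half of objective 3 is not estimated. The documents do not support that. SGRQ variation is fully covered, and the five dimensions and EQ VAS are described at enrolment, V3 and V5, so the course of the group can be read for all of them. What is missing from view is the within-patient VAS change with its spread, and the index.

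The possible distortion of a VAS comparison is 1 to 3 points at 20% drop-out and 2 to 6 points at 40%. This assumes that leavers start 5 to 15 points below completers, that all 200 patients have a baseline VAS, and that drop-out is the only source of missing forms. The size follows directly from the assumed gap and is an illustration, not an estimate. The objective is secondary and descriptive, so this is a correction worth making rather than a threat to the study.

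**What to change.** - Add to Table 26 the paired change from baseline in EQ VAS at V3 and V5: the usual descriptive statistics, n and 95% CI, in patients with both values. Label it as a completer estimate.
- Confirm that the index and its change are in the unpublished SAP text. If they are not, add the index at each visit and its paired change at V3 and V5. Name the scoring in SAP section 3, using the Italian population value set that the protocol cites (reference 48).
- If the sponsor chose to drop any of these, record it in the SAP as a departure from protocol 8.7.

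The cost is a few table rows and a short scoring definition. All the data are already collected at enrolment, 6 and 12 months.

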4.9 Ongoing therapies for IPF

Table 34. IPF treatments ongoing at enrollment

The table will provide:

- Frequency distribution of patients with at least one IPF pharmacological treatment ongoing at baseline [\[F09_THERAPY_IPF.THER_Pharma_YN\]](#).
- Frequency distribution of patients with at least one IPF non pharmacological treatment ongoing at baseline [\[F09_THERAPY_IPF.THER_non_pharma_YN\]](#).
- Frequency distribution of patients listed for lung transplantation at enrollment [\[F09_THERAPY_IPF.THER_transplant_YN\]](#).

stratified by type of therapy (therapy for IPF, IPF-exacerbations or IPF-related AEs).

Percentages will be computed out of the total number of patients evaluable at enrollment.

Table 35. IPF treatments ongoing at 3-month follow up

The table will provide:

- Frequency distribution of patients with at least one IPF pharmacological treatment ongoing at 3-month follow up.
- Frequency distribution of patients with at least one IPF non pharmacological treatment ongoing at 3-month follow up.
- Frequency distribution of patients listed for lung transplantation at 3-month follow up [\[F09_THERAPY_IPF.THER_transplant_fup_YN\]](#).

stratified by type of therapy (therapy for IPF, IPF-exacerbations or IPF-related AEs).

Percentages will be computed out of the total number of patients who performed the 3-month follow up.

Table 36. IPF treatments ongoing at 6-month follow up

The table will provide:

- Frequency distribution of patients with at least one IPF pharmacological treatment ongoing at 6-month follow up.
- Frequency distribution of patients with at least one IPF non pharmacological treatment ongoing at 6-month follow up.
- Frequency distribution of patients listed for lung transplantation at 6-month follow up [\[F09_THERAPY_IPF.THER_transplant_fup_YN\]](#).

stratified by type of therapy (therapy for IPF, IPF-exacerbations or IPF-related AEs).

Percentages will be computed out of the total number of patients who performed the 6-month follow up.

Table 37. IPF treatments ongoing at 12-month follow up

The table will provide:

- Frequency distribution of patients with at least one IPF pharmacological treatment ongoing at 12-month follow up.
- Frequency distribution of patients with at least one IPF non pharmacological treatment ongoing at 12-month follow up.
- Frequency distribution of patients listed for lung transplantation at 12-month follow up [\[F09_THERAPY_IPF.THER_transplant_fup_YN\]](#).

stratified by type of therapy (therapy for IPF, IPF-exacerbations or IPF-related AEs).

Percentages will be computed out of the total number of patients who performed the 12-month follow up.

4.10 Ongoing pharmacological therapies for IPF

Table 38. Distribution of patients according to IPF pharmacological treatments ongoing at enrollment

The table will provide the frequency distribution of IPF pharmacological treatments (actives) ongoing at enrollment (see 'Computed variables' chapter) stratified by type of therapy (therapy for IPF, IPF-exacerbations or IPF-related AEs).

A patient could receive more than one active.

Percentages will be computed out of the total number of patients evaluable at enrollment.

Table 39. Distribution of patients according to IPF pharmacological treatments ongoing at 3-month follow up

The table will provide the frequency distribution of IPF pharmacological treatments (actives) ongoing at 3-month follow up (see 'Computed variables' chapter) stratified by type of therapy (therapy for IPF, IPF-exacerbations or IPF-related AEs).

A patient could receive more than one active.

Percentages will be computed out of the total number of patients who performed the 3-month follow up.

Table 40. Distribution of patients according to IPF pharmacological treatments ongoing at 6-month follow-up visit

The table will provide the frequency distribution of IPF pharmacological treatments (actives) ongoing at 6-month follow up (see 'Computed variables' chapter) stratified by type of therapy (therapy for IPF, IPF-exacerbations or IPF-related AEs).

A patient could receive more than one active.

Percentages will be computed out of the total number of patients who performed the 6-month follow up.

Table 41. Distribution of patients according to IPF pharmacological treatments ongoing at 12-month follow-up visit

The table will provide the frequency distribution of IPF pharmacological treatments (actives) ongoing at 12-month follow up (see 'Computed variables' chapter) stratified by type of therapy (therapy for IPF, IPF-exacerbations or IPF-related AEs).

A patient could receive more than one active.

Percentages will be computed out of the total number of patients who performed the 12-month follow up.

Table 42. IPF pharmacological treatments from diagnosis to the end of observation period – Dosage regimen

The table will consider all the pharmacological treatments assumed by the patients for IPF, IPF-exacerbations or IPF-related AEs from diagnosis to the end of observation period. It will provide:

Descriptive statistics (mean, median, standard deviation, quartiles, min, max) of the IPF pharmacological treatment dosage per administration by Drug, Unit of administration, frequency of administration [[F23_IPF_PHARMACOLOGICAL_THERAPY.DRUG, UNIT_3,FREQ_ADMIN](#)] and duration of therapy (number of days).

Two separate tables will be provided: one for IPF pharmacological treatments ongoing at enrollment having/not having fixed-dose formulation [[F23_IPF_PHARMACOLOGICAL_THERAPY.DOSE_2](#)].

The patients evaluable at enrollment will be considered.

Table 43. Time between diagnosis and start of therapy for IPF

The table will provide the main descriptive statistics (mean, median, standard deviation, quartiles, min, max) of the time between diagnosis and start of therapy for IPF (weeks).

First therapy for IPF assumed by evaluable patients will be considered.

Only therapies for IPF will be considered.

4.11 Pharmacological therapies for IPF and exacerbations**Listing 44. Patients with exacerbations during observational period and therapy for IPF**

A listing of patients with at least one exacerbation during observational period will be shown. The therapy ongoing before the exacerbation and the therapy ongoing after the exacerbation will be shown; in case of no therapy, this will be indicated in the listing.

In case of more than one exacerbation all the above information (about therapy before and after the exacerbation) will be shown referring to each exacerbations.

4.12 Ongoing non pharmacological therapies for IPF**Table 45. IPF non pharmacological therapy ongoing at enrollment**

The table will provide the frequency distribution of IPF non pharmacological therapies (long-term oxygen therapy, cardiopulmonary exercise training or psychological support) ongoing at enrollment (see 'Computed variables' chapter) stratified by type of therapy (therapy for IPF, IPF-exacerbations or IPF-related AEs).

Percentages will be computed out of the total number of patients evaluable at enrollment.

Table 46. Distribution of patients according to IPF non pharmacological therapy ongoing at 3-month follow up

The table will provide the frequency distribution of IPF non pharmacological therapies (long-term oxygen therapy, cardiopulmonary exercise training or psychological support) ongoing at 3-month follow-up visit (see 'Computed variables' chapter) stratified by type of therapy (therapy for IPF, IPF-exacerbations or IPF-related AEs).

Percentages will be computed out of the total number of patients who performed the 3-month follow up.

Table 47. Distribution of patients according to IPF non pharmacological therapy ongoing at 6-month follow-up visit

The table will provide the frequency distribution of IPF non pharmacological therapies (long-term oxygen therapy, cardiopulmonary exercise training or psychological support) ongoing at 6-month follow-up visit (see 'Computed variables' chapter) stratified by type of therapy (therapy for IPF, IPF-exacerbations or IPF-related AEs).

Percentages will be computed out of the total number of patients who performed the 6-month follow up.

Table 48. Distribution of patients according to IPF non pharmacological therapy ongoing at 12-month follow-up visit

The table will provide the frequency distribution of IPF non pharmacological therapies (long-term oxygen therapy, cardiopulmonary exercise training or psychological support) ongoing at 12-month follow-up visit (see 'Computed variables' chapter) stratified by type of therapy (therapy for IPF, IPF-exacerbations or IPF-related AEs).

Percentages will be computed out of the total number of patients who performed the 12-month follow up.

Table 49. IPF non pharmacological therapy from diagnosis to the end of observation period – Number of sessions of cardiopulmonary exercise training or psychological support

It will provide the descriptive statistics (mean, median, standard deviation, quartiles, min, max) of the total number of sessions of cardiopulmonary exercise training or psychological support performed from diagnosis to the end of observation period **[F24_NON_PHARMACOLOGICAL_THERAPY.N_SESSIONS]** by therapy **[F24_NON_PHARMACOLOGICAL_THERAPY.THERAPY]**.

The patients evaluable at enrollment will be considered.

Table 50. Long term Oxygen therapy from diagnosis to the end of observation period – Dosage regimen

The table will consider all the long-term oxygen therapies assumed by the patients for IPF, IPF-exacerbations or IPF-related AES from diagnosis to the end of observation period.

It will provide the descriptive statistics (mean, median, standard deviation, quartiles, min, max) of the flow (L/min) **[F24_NON_PHARMACOLOGICAL_THERAPY.FLOW]** by Drug **[F24_NON_PHARMACOLOGICAL_THERAPY.DRUG]**, Hours per day **[F24_NON_PHARMACOLOGICAL_THERAPY.HOURS]** and duration of therapy (number of days).

The patients evaluable at enrollment will be considered.

4.14 AEs and ADRs between diagnosis and end of observation**Table 52. Patients with AEs and ADRs between diagnosis and end of observation**

The table will provide the absolute and relative frequency of the patients with at least one adverse events between diagnosis and end of observation.

The total number of evaluable patients at enrollment will be considered.

Listing 53. AEs and ADRs between diagnosis and end of observation

The table will provide the distribution of every AE or ADR, occurred between diagnosis and end of observation by serious AE, seriousness category and causal relationship with Nintedanib.

The total number of evaluable patients at enrollment will be considered.

